5.4 Subject Withdrawal

5.4.1 *Reasons for Withdrawal*

Practitioners and patients are free to withdraw from participation in the study at any time upon request.

5.4.2 *Handling of Patient Withdrawals*

In the case of patient withdrawal from the study, staff will only attempt continued follow-up data collection for patients who are withdrawn due to an unanticipated problem (UP). In these circumstances, only data related to the completion of reporting requirements for the UP will be recorded. For patients withdrawn from the study for any other reason, the date and reason for withdraw will be recorded and no additional study data will be collected. Patients withdrawn from the study may continue to receive usual dental care as patients of the participating dentists, however, additional study data will not be collected from continuation of the usual clinical care (except as noted above).

Replacement of patients who withdraw or discontinue early will be allowed, but only during the initial 2-4-month patient enrollment period for each practitioner. The practitioner may attempt to enroll one replacement patient for each patient enrolled who withdraws or discontinues during the practitioner-specific enrollment period.

5.5 Premature Termination or Suspension of Study

This study may be suspended or prematurely terminated if there is sufficient reasonable cause. Written notification, documenting the reason for study suspension or termination, will be provided by the suspending or terminating party. If the study is prematurely terminated or suspended, the SPI will promptly inform the IRB and will provide the reason(s) for suspension or termination.

Circumstances that may warrant termination include, but are not limited to:

- Determination of unexpected, significant, or unacceptable risk to subjects.
- Insufficient adherence to protocol requirements.
- Data that are not sufficiently complete and/or evaluable.
- Determination of futility.

6 STUDY SCHEDULE

The practitioners enrolled in the National Dental PBRN who express interest in the study will be invited to participate. Study information and instructions will be provided by regional staff to interested practitioners. A detailed Practice Training Binder will be provided to each practice in written form prior to initiation of the study in the practice. The Practice Training Binder will carefully describe the subject selection procedures,

methods for approaching subjects and obtaining Informed Consent, methods for data collection, and other study procedures. A summary flow chart will be sent to the practices with a description of the enrollment and baseline visits and an overview flow chart of the study. This will provide a simple, single page reference for office personnel involved in the study. In addition, in-person meetings (or teleconferences) with office staff will be held to provide further instruction in completing CRFs. The RC will also meet (or have an individual telephone call) with the participating practitioners prior to initiating the study to make sure that they and their office staff understand the study procedures.

The RCs will be in close contact with practitioners prior to the study initiation to ensure that the practitioner and his/her office staff are familiar with study procedures.

The study will proceed in the following stages:

- 1) Each region will enroll approximately 30 practices into the study;
- 2) Practice personnel will receive any necessary IRB training prior to starting the study;
- 3) Practitioner informed consent process (if required by that region's IRB), Individual Investigator Agreements, University of Alabama at Birmingham (UAB) Master Service Agreement, and similar documents will be obtained prior to the start of the study;
- 4) Practitioners will complete the online practitioner questionnaire;
- 5) RCs will ensure practices are trained in the appropriate study procedures (see below); and
- 6) Practitioners will screen and enroll eligible study patients into the study.

The CC along with the RAS and RCs will coordinate the launch of the study. After the participating practitioner has undergone informed consent procedures and has completed the online practitioner questionnaire, and when the practice has been trained by the RC in appropriate study procedures, the practice would be ready to recruit patients into the study. It is desirable that within each practice, the patient enrollment is performed in a 2-4-month period, so that the practice can maintain its focus on data collection for this study. The enrollment period will be based on number of eligible patients seen per month by the practitioner. The entire enrollment period will take approximately 4-6 months to complete for six regions.

6.1 Practitioner Enrollment/Baseline

- Obtain and document consent from practitioner participant according to regional IRB requirements.
- Verify practitioner inclusion/exclusion criteria.

- Obtain practitioner online questionnaire data.

6.2 Patient Screening

A prospective study patient may be recruited at any dental appointment in the dental office participating in the study. A patient who indicates oral pain by self-report and meets the inclusion criteria may be eligible for participation in the study. Assessment of study inclusion will involve: a) Reviewing medical conditions and medication usage specified as study exclusion criteria, b) Performing an oral examination to rule-out oral conditions that warrant study exclusion, and c) Confirming a diagnosis of DH. A diagnosis of DH will be based on the following from the patients' history and clinical examination: 1) Patient's self-report of tooth pain, and 2) Practitioner's exclusion of other dental and periodontal conditions that may be etiologies of tooth pain. Conditions that need to be ruled out when diagnosing dentin hypersensitivity are listed in the exclusion criteria in Section 5.2. If study inclusion criteria are met, and a patient expresses interest in the study, the designated office staff will introduce the study to the patient. Enrollment and baseline study procedures will occur at the same dental visit at which eligibility is confirmed.

The procedures listed below are consistent with those included in the Schedule of Events (Appendix A).

6.3 Enrollment/Baseline

Patients who agree to participate in the study and meet the inclusion criteria will be enrolled in the study. The regionally-approved consent process will be completed by a designated office staff member, most likely the dentist.

If an eligible patient declines participation in the study, this occurrence will be noted in the patient log and the informed consent process will not be completed; it will be considered as failure to provide informed consent.

Enrollment/Baseline Visit (Visit 1, Day 0, time of this visit is denoted by t_{1_0})

- Obtain and document consent from patient according to regional IRB requirements.
- Verify inclusion/exclusion criteria.
- Obtain patient contact information and preferred method of contact.
- Obtain patient demographic data.
- Obtain patient self-reported pain assessments.
- Record results of dental examinations related to DH.
- Record treatment recommendations and treatment administered/prescribed.

6.4 Intermediate Follow-up Assessments

The data will be completed by patients online on the designated webpage or by completing a printed questionnaire and mailing it to the designated RCs.

Follow-up Assessment 1, Day 7 (-6 days to +6 days) (t_{1_1})

- Patients will complete pain assessment/compliance to treatment questionnaire.

Follow-up Assessment 2, Day 28 (-6 days to +6 days) (t_{1_2})

- Patients will complete pain assessment/compliance to treatment questionnaire.

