3.2 Study Outcome Measures

3.2.1 Primary Outcomes

To characterize diagnosis and treatment of DH in the practice setting, practitioners' preferred methods of diagnosing and treating DH will be ascertained via a practitioner

online questionnaire to be completed upon study enrollment and via practitioner data collection forms during patient visits.

Diagnosis of dentin hypersensitivity:

Online practitioner questionnaire: Practitioners' preferred diagnostic procedures that are usually implemented when diagnosing DH in the practice setting will be ascertained. These will include: spontaneous patient report, patient report after dentist's query, applying air blast, applying cold water, scratching dentin with dental explorer, requesting numeric descriptor of pain, requesting visual scale descriptor of pain, and using an electric pulp tester.

Treatment modalities:

Online practitioner questionnaire: Practitioners' preferred method of treatment of DH and the rationale for the elected treatment or treatments will be ascertained. Questions will include preferred treatment modalities (see below) and approach(es) to treatment of DH (i.e., providing multiple treatments at one time, one treatment or staged approach, no treatment, and/or no advice).

Patient visit(s): The usual and customary treatment(s) for DH utilized by the participating practitioner will be applied or prescribed and recorded.

The following groups of treatment modalities will be ascertained:

1. Fluoride products (gels, varnishes, pastes, rinses)
2. Desensitizing over the counter (OTC) Potassium nitrate toothpastes
3. Glutaraldehyde/HEMA products
4. Bonding agents
5. Sealants
6. Restorative treatments
7. Lasers
8. Oxalates
9. No treatment
10. Advice
11. Other

Patient-reported pain outcomes:

Patient visit(s) and follow-up: Patient-reported pain outcomes will be assessed by changes in patient report of pain intensity, duration, and frequency. Patients' perception of pain will be assessed by the Visual Analog Scale (VAS) at baseline, 1 week-, 4 weeks- and 8 weeks- post-baseline. Duration, intensity, tolerability and pain description changes will be assessed by means of the Labeled Magnitude (LM) scales at baseline, 1 week-, 4 weeks- and 8 weeks- post-baseline (Heaton et al., 2013). If patients return

for a second- or third-line of treatment, these pain assessments will be implemented also at 1, 4 and 8 weeks after the initiation of the second- or third-line of treatment.

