6.5 Final Follow-up Assessment

Final Follow-up Assessment 3, Day 56 (-6 days to +6 days) (t_{1_3})

Patients will complete pain assessment/compliance/satisfaction with treatment questionnaire.

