7.2 Questionnaire Administration

Prior to enrolling study patients, participating practitioners will complete an online practitioner questionnaire that will ascertain modalities used to diagnose DH as well as treatment modalities and approaches towards treatment of DH (see Section 3.2).

Practitioners will be asked about their patients' predisposing and enabling variables at/ or soon after the baseline visit (see Section 3.2.2).

At the baseline visit after the oral examination, patients will complete a pain assessment questionnaire that will ascertain the pain intensity, frequency, and duration. Patients will record pain levels by using LM pain scales that were developed at the University of Washington specifically to assess the pain associated with DH (Heaton et al., 2013). These four 100-millimeter (mm) horizontal scales are labeled with descriptive terms to assess the intensity, duration, tolerability and description of the participant's pain experience. Patients will also complete a standard 100-mm horizontal VAS on which the endpoints are marked "not painful" and "most intense pain sensation imaginable."

The clinical symptom of DH is likely associated with the "overall patient experience" because there is likely spatial summation. When an individual drinks cold fluids, for example, his/her DH/pain would be associated with multiple teeth (if multiple teeth are sensitive). Rating each tooth could only be achieved if the dentist systematically isolated each tooth and stimulated each one separately -- which doesn't mimic the clinical condition. The VAS/LM ratings will be applied to assess the overall patient pain experience associated with DH. The LM pain scales capture specific dimensions of pain that characterize the DH pain response (Heaton et al., 2013).

At 1-, 4- and 8- weeks post-baseline and/or second/third-line treatment visit(s), pain intensity, frequency, and duration will be re-ascertained as described above to measure patient-reported pain outcomes via an online or mailed questionnaire. Compliance with treatment will also be assessed via one Likert-like question. Treatment satisfaction will be assessed by one VAS question 8-weeks post the last treatment visit.

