15.3 Types of Data

Data for the present study consist of the following:

- Practitioner-level data from the National Dental PBRN enrollment questionnaire and the study online practitioner questionnaire,
- Patient characteristics data from baseline questionnaire,
- Patient-, pain-, treatment compliance-, and satisfaction follow-up assessments, and
- Unanticipated problems data (collected in the main study database).

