Appendix A. Schedule of Events

Appendix B. Subject Retention Plan

Appendix C. Quality Management Plan

Appendix D. Data Management Plan

Appendix A: Schedule of Events

Procedures	Baseline Study Visit				2 nd -Line Treatment Visit				3 rd -Line Treatment Visit				Premature Discontinuation/ Withdrawal
	Enrollment/Baseline (Day 0)	1 Wk Follow-up (Day 7, -6 to +6)	4 Wk Follow-up (Day 28, -6 to +6)	8 Wk Follow-up (Day 56, -6 to +6)	2 nd -Line Treatment	1 Wk Follow-up (Day 7, -6 to +6)	4 Wk Follow-up (Day 28, -6 to +6)	8 Wk Follow-up (Day 56, -6 to +6)	3 rd -Line Treatment	1 Wk Follow-up (Day 7, -6 to +6)	4 Wk Follow-up (Day 28, -6 to +6)	8 Wk Follow-up (Day 56, -6 to +6)	
Obtain Informed Consent	X												
Assessment of Eligibility Criteria	X												
Review of Medical/Dental History	X												
Obtain/confirm contact information and preferred method of contact	X				X				X				
Oral Examination	X				X				X				
Patient Demographics (in office)	X												
Pain Assessment (in office)	X				X				X				X ¹
Treatment prescribed and/or performed	X				X				X				
Follow-up Pain Assessment (online or mail)		X	X	X		X	X	X		X	X	X	
Compliance with treatment		X	X	X		X	X	X		X	X	X	X ¹
Satisfaction with treatment				X				X				X	X ¹

¹ Obtain only if withdrawal occurs during an in-office visit and consent is not withdrawn.

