- 1) The method described under Methods to Minimize “Lost”, first point, will also help reduce the number of subjects who refuse to continue participating. At enrollment, subjects are informed that they are agreeing/consenting to participate in a longitudinal study. Subjects who enroll are required to state a willingness to participate throughout the study.

- 2) The method described under Methods to Minimize “Lost”, third point (making contact prior the follow-up assessment interval), should also help reduce refusals. Additionally, follow-up involvement will be kept as light and convenient for the subject as possible.

Methods to Minimize “Unable”

- 1) There are several scenarios in which a subject stops seeing the original/enrolling practitioner:
 - a. Subject does not move, but:
 - i. Subject changes dentists- in same practice
 - ii. Subject changes dentists- in different practice
 - iii. Subject stops seeing any dentist
 - b. Subject moves
 - i. Subject sees new dentist
 - ii. Subject stops seeing any dentist
 - c. Dentist retires or dies
 - d. Dentist moves
 - e. Dentist refuses to continue participating (shouldn't happen)
- 2) The operational impact of all of the above scenarios can be summarized by two scenarios:
 - a. Subject has a new dentist (not a National Dental PBRN member)
 - b. Subject stops seeing any dentist
- 3) Locating the subject should not be a problem (see Methods to Minimize “Lost”), and having the subject agree to continue participating should not be a problem (see Methods to Minimize “Refused”).
- 4) The main operational issue is: How to get study follow-up assessment information from subjects seeing a non-National Dental PBRN dentist or not seeing any dentist.
 - a. Actively recruit the new dentist into the Network so the subject can continue to be followed by the new dentist.
 - b. Request permission from the new office to complete a chart abstraction to obtain data.

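### As described, the follow-up forms miss sensitivity products and outside dental care started after baseline, so co-treatment that differs by modality can distort the pain comparisons

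*Protocol*

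**What the plan says.** **Treatment.** Section 3.2.1 ties recording to office visits: "The usual and customary treatment(s) for DH utilized by the participating practitioner will be applied or prescribed and recorded". In Appendix A the row "Treatment prescribed and/or performed" is marked at the baseline, second-line and third-line visits and at none of the 1-, 4- or 8-week follow-ups. Sections 6.3 and 6.6 agree. Previous and current treatment is asked about once, at or soon after baseline (section 3.2.2).

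**Follow-up.** The home assessments cover pain and compliance at weeks 1 and 4 ("Patients will complete pain assessment/compliance to treatment questionnaire", section 6.4) and add satisfaction at week 8 ("Patients will complete pain assessment/compliance/satisfaction with treatment questionnaire", section 6.5). Section 15.3 lists the follow-up data as "Patient-, pain-, treatment compliance-, and satisfaction follow-up assessments". Section 7.2 says "Compliance with treatment will also be assessed via one Likert-like question", and section 3.2.2 makes clear that this question is about following the practitioner's recommendation.

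**Analysis.** The modality list in section 3.2.1 includes "Desensitizing over the counter (OTC) Potassium nitrate toothpastes", no treatment and advice. For the third primary objective, section 11.2 puts modality in the model as a fixed effect and gives primary interest to the time-by-treatment interaction. It adds that differences between groups reflect differences between treatment effects, because causes shared by both groups drop out.

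**The concern.** One of the analysed modalities is a toothpaste that any patient can buy without a visit. A patient recorded under no treatment, advice or an in-office procedure may start it at home, or be treated elsewhere, and nothing in the described follow-up would show it. Later pain ratings would still be analysed under the modality recorded in the office.

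The cancelling argument in section 11.2 covers only causes that act equally on the groups being compared. Co-treatment taken up more often under one modality than another does not cancel. It becomes part of what is read as a treatment-effect difference. Section 2.2 hopes the study will show which products are effective and feed into guidelines, so that reading has consequences. Because the gap is in data collection, no later analysis plan could fill it.

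**Working it through.** **Step 1. What is and is not captured, as the protocol describes it.**

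- Treatment in progress at baseline: captured once (section 3.2.2).
- A product the participating dentist recommends, prescribes or applies: captured at that visit (sections 3.2.1 and 6.3).
- Return to the enrolling dentist within the window: captured as a new line of treatment, and follow-up restarts (sections 4 and 6.6).
- Care from a new dentist outside the network: captured only if that dentist is recruited or permits a chart abstraction (Appendix B).
- A product the patient starts unprompted, or other outside care: no described route.

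**Step 2. Reproduce the plan's figures.** Inputs from section 11.1: 180 dentists, m = 10 to 20 patients each, ICC 0.00 to 0.05, two equal groups, 5% type I error (taken as two-sided), 80% power.

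- Effective N = 180m / [1 + (m − 1) × ICC]
- Detectable difference in SD units = (1.96 + 0.84) × √(2/n), with n = effective N / 2

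- m = 20, ICC 0: N = 3,600, giving 0.093 SD (the protocol states 0.095).
- m = 10, ICC 0.05: N = 1,800 / 1.45 = 1,241, giving 0.159 SD (the protocol states 0.160).

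Power for 0.5 SD exceeds 99.99% in both cases. The plan's figures are reproduced.

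**Step 3. Basis for the illustration.** m = 14, ICC 0.05: N = 2,520 / 1.65 = 1,527, so n is about 764 per group and the standard error of a difference is √(2/764) = 0.051 SD. The protocol gives no rate of unrecorded co-treatment, so every rate below is an assumption. The calculation is a two-group comparison at a single rating, without multiplicity adjustment.

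**Step 4. Spurious difference.** Suppose two modalities are equally effective, but use of an unrecorded product worth 0.5 SD differs between them by d. Apparent difference = 0.5 × d.

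| d | Apparent difference | Chance of a significant result (nominal 5%) |
|---|---|---|
| 10 points | 0.05 SD | 16% |
| 20 points | 0.10 SD | 50% |
| 30 points | 0.15 SD | 83% |

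**Step 5. Dilution.** Suppose instead that a fraction c of the comparison group only takes a product that reproduces the whole treatment difference before the rating. Apparent difference = true difference × (1 − c).

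| c | True 0.5 SD appears as (power) | True 0.2 SD appears as (power) |
|---|---|---|
| 0% | 0.50 (>99%) | 0.20 (97%) |
| 10% | 0.45 (>99%) | 0.18 (94%) |
| 20% | 0.40 (>99%) | 0.16 (88%) |
| 30% | 0.35 (>99%) | 0.14 (78%) |

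Steps 4 and 5 move the comparison in opposite directions. Which applies depends on who takes up what, and the protocol gives no information on that.

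**The case against.** **The forms are not shown.** Their content is inferred from how the protocol describes them, and section 15.2 says the case report forms are still to be developed. This stands as a limit on the claim. However, sections 6.4, 6.5, 7.2, 15.3 and Appendix A give the same consistent content.

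**Much care is captured.** A reader might infer that any care started during follow-up is credited to the first modality. The documents do not support that. A return to the enrolling dentist within the window is recorded, and the earlier line's follow-up stops. A reader might also note that treatment is recorded on one day of a 56-day follow-up. That is not a measure of exposure coverage, because a treatment recorded on Day 0 can continue and compliance is asked three times.

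**Power is ample.** This stands for the planned medium effect: even halved to 0.25 SD it keeps more than 99% power. Inflation of the required sample size is therefore not a practical argument here. Bias is a different matter, since a large sample makes a spurious difference easier to declare.

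**The illustrations are simplified.** A product started in week 6 cannot affect the week 1 or week 4 ratings, and the dilution formula assumes the product reproduces the whole difference. Both points stand.

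**The study is observational and estimation-driven.** What patients do after advice or no treatment is arguably part of usual management. As a description of pathways that is fair. It does not cover the sentence in section 11.2 that reads group differences as differences between treatment effects.

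**Conclusion.** The point holds in a limited form. As described, follow-up does not capture self-bought desensitising products or outside dental care started after baseline, except through a conditional chart abstraction after a change of dentist. Co-treatment that differs by modality could shrink real differences or create spurious ones in the comparison of primary interest for pain.

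It is tempting to conclude that the bias runs toward zero and flatters no treatment and advice, on the ground that patients still in pain are the likeliest to buy a product. That is plausible, but the protocol contains nothing from which size or direction can be derived. The figures of 0.05 to 0.15 SD, significant about 16% to 83% of the time, rest on an assumed product effect of 0.5 SD, an assumed 10- to 30-point difference in use, 14 patients per dentist, ICC 0.05 and two equal groups. They show that the bias could matter, not that it will.

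**What to change.** 1. Add one item to the existing 1-, 4- and 8-week forms, with a matching row in Appendix A. It asks whether, since the last form, the patient has started any other product or received any other dental care for sensitive teeth, with a checklist of the section 3.2.1 modalities and a start date. If the forms already contain such an item, the protocol need only say so.
2. Report co-treatment by modality and assessment time.
3. Repeat the time-by-treatment analysis as a sensitivity analysis that accounts for reported co-treatment. State that starting a product probably depends on persistent pain, so dropping later ratings is informative censoring and a time-varying term is affected by earlier pain. The result is therefore descriptive.
4. Qualify the sentence in section 11.2: only causes common to both groups cancel, and co-treatment that differs by modality does not.

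The cost is slightly longer forms, review of the amendment by the regional IRBs (section 14.2), and some risk that the question itself prompts product use. Usual care is not otherwise changed.
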